5 OBJECTIVES

5.1 Primary objective

• To evaluate the safety and reactogenicity of two dose levels of WRAIR's AMA1 malaria antigen (FMP2.1) adjuvanted in GlaxoSmithKline Biologicals' AS02A compared to rabies vaccine in malaria-experienced Malian adults aged 18-55 years inclusive.

5.2 Secondary objectives

1. To measure the magnitude and duration of antibody response to FMP2.1

Page 29 of 96 Version 17, DEAP/MRTC/MMVDU CONFIDENTIAL

- 2. To measure cellular immune responses to FMP2.1 at baseline and after immunization
- 3. To measure the inhibition of parasite growth by the in vitro GIA

4. To determine the specificity of the antibodies to diverse AMA1 genotypes in addition to 3D7, by measuring by ELISA, and GIA on parasites with typed AMA1.

6 STUDY DESIGN AND METHODOLOGY

6.1 Overview

- Double blind, randomized controlled dose escalation phase I study
- One study center
- Screening will be done within 35 days prior to the first immunization
- Dose escalating by approximately 25µg and 50µg of FMP2.1 adjuvanted with 0.25 mL and 0.5 mL of AS02A, respectively
- At each of the two FMP2.1 dose levels, 30 adults will be randomized to receive either FMP2.1/AS02A (n=20) or RabAvert® vaccine (n=10)
- Immunization schedule will be on study days 0, 30 + 7, and 60 + 7
- Each consecutive immunization with the 50 µg dose of FMP2.1 will be administered at least 14 days after the corresponding immunization with the 25 µg dose of FMP2.1 to permit review of day 7 safety laboratory results
- Route of immunization will be the deltoid muscle IM
- CRFs will serve as source documents. Only information that cannot be collected initially onto CRFs (namely, clinical laboratory test results and adverse event medical records) will first be collected onto separate source documents prior to transcription into CRFs.
- Study duration will be approximately 12 months per participant
- 7-day surveillance (day of vaccination and study days 1, 2, 3 and 7 for solicited adverse events
- 30-day surveillance for unsolicited adverse events
- Follow-up of serious adverse events (SAEs) until resolution
- Beginning Study Day 120, participants will be visited and assessed by local guides at home at monthly intervals and will be asked to return to clinic every 3 months for safety surveillance.
- The primary analysis will be conducted for all primary and secondary endpoints at a datalock-point one month post Immunization 3 (study day 90), after which the Primary Study Report will be produced.
- The study will then continue in a single-blind fashion. Data gathered during this period will be reported in an addendum report.
- At the end of the study participants will be informed which vaccine they received and those who received malaria vaccine will be offered immunization with the rabies vaccine.

6.2 Site description

The study will be conducted in Bandiagara, which has been the site of MRTC malaria clinical, epidemiological and entomological studies since 1993. Since 1998 Bandiagara has been the site of an NIH-supported contract for developing a site for testing malaria vaccines, known as

Page 30 of 96 Version 17, DEAP/MRTC/MMVDU CONFIDENTIAL

the Bandiagara Malaria Project (BMP). The BMP has completed full censuses of Bandiagara, established a laboratory with the capability of preserving sera, PBMCs, live parasites and DNA; and a clinical research center where malaria diagnosis and hemoglobin and blood glucose levels are routinely determined and where children with severe malaria are hospitalized and cared for. The BMP conducted a case control study that enrolled 253 cases of severe malaria matched to 253 each of uncomplicated malaria and healthy controls. A cohort study of 427 subjects aged 3 months to 20 years with nested drug resistance studies was conducted from 1999 through 2001 as well as a matched cohort incidence trial of 338 pairs or 676 children from 2002-2004 to monitor the effects of concomitant schistosomiasis on malaria acquisition. The rate of loss to follow-up has consistently been less than 7%. The BMP clinical facilities are located within the Bandiagara District health center, where a two large blocks of rooms were renovated in 2003 for a Phase 1 malaria vaccine trial, "Double blind randomized controlled Phase 1 trial to evaluate the safety and immunogenicity of WRAIR's MSP1 candidate malaria vaccine (FMP1) adjuvanted in GlaxoSmithKline Biologicals' AS02A vs. Rabies vaccine in semi-immune adults in Bandiagara, Mali" The clinical research facility includes an air-conditioned clinical laboratory and vaccine storage preparation room, six private consultation rooms, a procedure room, covered waiting area, two vaccination rooms, a resuscitation suite, an observation room, and storage and administrative space. Directly across the road is the Bandiagara Center for Research on Traditional Medicine, where two rooms are exclusively used for BMP laboratory activities. Locked cabinets with restricted access are used for data storage.

The BMP team has been trained to conduct GCP-compliant studies, using source documents, written informed consent and standardized case report forms. The BMP team has also established a strong trust and rapport with the community, and the community is very accepting of conducting malaria vaccine trials there.

The site is being connected to the MRTC central laboratory in Bamako via a VSAT system, which will allow a high-speed communication link with Bamako, U.S. partner institutions and the Internet.

6.2.1 Determination of local clinical laboratory test reference ranges

In most African countries, reference ranges for clinical laboratory tests are those used in clinical laboratories from Europe and the United States. Laboratory tests such as hemoglobin concentration, white blood cell count, platelet count, serum creatinine and liver enzymes concentration, which are used to determine malaria vaccine potential toxicity, have a different distributions in the West African populations than in European and American populations (61). A survey was therefore undertaken in Bandiagara in March 2003, to determine local reference intervals for clinical laboratory values. This survey followed the methods described in the National Committee for Clinical Laboratory approved guidelines (NCCLS) (62). 120 each healthy male and female residing in Bandiagara were included and reference limits were calculated nonparametrically by taking the 2.5 and 97.5 percentiles of the observed sample values. The 95% confidence intervals of the reference limits were also calculated. The reference intervals calculated were used to establish the upper limits of normal ranges to determine locally appropriate exclusion criteria and toxicity ranges for adverse events for this trial.

6.2.2 Competencies of staff

Page 31 of 96 Version 17, DEAP/MRTC/MMVDU CONFIDENTIAL

The BMP clinic team is composed of medical doctors and doctors of pharmacy who are experienced in conducting complex studies with long periods of follow-up and complying with ICH/GCP requirements. Malian and U.S. investigators on this protocol have worked in close collaboration at this field site since 1997. Past studies have been implemented with the aim of preparing the team to conduct GCP-compliant malaria vaccine trials, culminating in a Phase 1 trial of a blood stage malaria vaccine conducted in 2003 through 2004. The team's training program in recent years has included GCP workshops in Mali, in Baltimore at the University of Maryland's Center for Vaccine Development, and at the Johns Hopkins Summer Institute on Biostatistics and Epidemiology. Several of the study investigators have attended courses and workshops on bioethics. Each year since 2002 MRTC investigators have attended a GCP workshop directed by the PI on this protocol and other senior MRTC investigators, and specific training on each clinical trial protocol and its study procedures are conducted. A specific training program on protocol-specific study procedures will be designed for the local guides and supporting staff in Bandiagara. The PI, co-investigators and the BMP clinic team will carry out all the study procedures. The local guides have many years of experience with the conduct of clinical research, and the senior guide is also trained as a nurse. Local guides will be provided with study-specific training, and are fluent in French as well as many local languages and dialects. They will have the responsibility to maintain contact with study participants, to remind them of their scheduled clinic visits, to guide them through the clinical research center from post to post (e.g. from vaccination room to observation room) and to document any travel outside the area of Bandiagara.

The U.S.-based clinical investigators have extensive experience with domestic and foreign vaccine trials as well as other clinical trials and field research in Africa and many other tropical regions. The U.S. co-PI was present for each immunization of the 2003 FMP1/AS02A Phase 1 trial in Mali, each time accompanied by one or more experienced clinical investigators from the CVD, WRAIR, and/or GSKBio. A similar level of close collaboration between Malian, U.S. and European investigators will be employed for this trial.

The Biostatistics and Epidemiology Unit of the MRTC is directed by senior investigators who hold graduate degrees in epidemiology and biostatistics from U.S. universities and staffed by five data entry technicians. The Unit has implemented data management systems based on 21 CFR 11 guidelines, and this will be their third malaria vaccine trial conducted under IND regulatory standards. The CVD statistician who will provide back-up and oversight of the data management and analysis process has decades of experience as the biostatistician for domestic and foreign Phase 1, 2, 3 and 4 vaccine trials.

6.3 Inclusion criteria

- A male or non-pregnant female aged 18-55 years inclusive at the time of screening.
- For women, willingness not to become pregnant until 1 month after the last immunization (pre-menopausal female participants will be referred to the local family planning clinic in Bandiagara, which offers several means of contraception that are approved and recommended by the Malian Ministry of Health)
- Separate written informed consent obtained from the participant before screening and study start, respectively
- Available and willing to participate in follow-up for the duration of study (12 months)

6.4 Exclusion criteria

The following criteria will be checked at the time of study entry (i.e. following screening, at the time that participants are enrolled into the vaccine trial itself). If any apply at the time of study entry, the subject will not be included in the study:

- Previous vaccination with any investigational vaccine or with any rabies vaccine
- Use of any investigational or non-registered drug or vaccine other than the study vaccine(s) within 30 days preceding the first study immunization, or planned use up to 30 days after the third immunization
- Chronic administration (defined as more than 14 days) of immuno-suppressants or other immune-modifying drugs within six months prior to the first immunization. This will include any dose level of oral steroids or inhaled steroids, but not topical steroids
- Planned administration/administration of a vaccine not foreseen by the study protocol within 30 days before the first study immunization with the exception of tetanus toxoid
- Any confirmed or suspected immunosuppressive or immunodeficient condition, including human immunodeficiency virus (HIV) infection
- Any confirmed or suspected autoimmune disease
- History of allergic reactions or anaphylaxis to immunizations or to any vaccine component
- History of serious allergic reactions to any substance, requiring hospitalization or emergent medical care
- History of allergy to tetracycline, doxycycline, nickel, Imidazole, chicken eggs, processed bovine gelatin, chicken protein, neomycin, or amphotericin B.
- History of splenectomy
- Serum ALT \geq 43 IU/L
- Serum creatinine level >113 μ mol /L for males and 70 μ mol /L for females
- Hb <11 g/dL for males and <10 g/dL for females
- WBC $< 4.0 \times 10^3$ /mm³ or $> 13 \times 10^3$ /mm³
- Absolute lymphocyte count $\leq 1.4 \ge 10^3 / \mu l$
- Thrombocytopenia < 108,000/µl
- More than trace protein, more than trace hemoglobin or positive glucose in urine
- Administration of immunoglobulins and/or any blood products within the three months preceding the first study immunization or planned administration during the study period.
- Suspected or known current alcohol or illicit drug abuse
- Pregnancy or positive urine beta-HCG on the day of or prior to immunization
- Breastfeeding
- Simultaneous participation in any other interventional clinical trial
- Acute or chronic pulmonary, cardiovascular, hepatic, renal or neurological condition, or any other findings that in the opinion of the PI may increase the risk of participating in the study
- Other condition that in the opinion of the PI would jeopardize the safety or rights of a participant in the trial or would render the participant unable to comply with the protocol

6.4.1 Justification for the exclusion of children

The FMP2.1/AS02A vaccine has been tested in 23 adults in the United States, and this will be its first use in a malaria-exposed population. Natural malaria transmission may affect

Page 33 of 96 Version 17, DEAP/MRTC/MMVDU CONFIDENTIAL

both the safety and immunogenicity of the vaccine, therefore it is felt that it is more ethical to perform this Phase 1 study first in adults who can give full, informed independent consent. Following this study, assuming the vaccine is shown to be safe and immunogenic in this study population, further studies in children are anticipated.

6.4.2 Rationale for using clinical assessment of immunosuppression

We do not plan to test for HIV at the time of screening. HIV seroprevalence is 1.7% in Mali, one of the lowest rates in sub-Saharan Africa. Although no serosurveys have been done in Bandiagara itself, this site is in a remote rural area and almost certainly has a lower prevalence rate than the average for the entire country. After working at this site for the past seven years, we have only very rarely encountered persons with illnesses that raised clinical suspicion of an immunosuppressive disease. Therefore, the training of staff and establishment of programs that would be necessary for voluntary counseling and testing for HIV would likely yield few, if any, cases of HIV in this small study.

Second, this study has been designed to produce comparable results to other Phase 1 trials of recombinant protein blood stage malaria vaccines adjuvanted with AS02A, including trials of FMP1/AS02A conducted in Kenya and Mali. In these studies, a similar approach was taken to exclude persons with clinical evidence of immunosuppressive disease but not test for asymptomatic HIV infection, based on the rationale that it is necessary to assess the safety and immunogenicity of this vaccine in generally healthy adults who are representative of the population from which they are drawn. In Kenya, where rates of HIV infection are higher, this general population includes many persons living with HIV and a study that excluded them would be of less value. Eventually, it will be necessary to demonstrate the safety and immunogenicity in persons living with HIV for any malaria vaccine to be employed in Africa, but because of the low rates of HIV infection in Mali these studies will have to be conducted elsewhere, and meaningful subanalyses of HIV-infected and uninfected vaccinees will require the larger sample sizes of Phase 2b or Phase 3 trials.

6.5 Treatments that could interfere with vaccine-induced immunity

The following criteria will be checked at each visit. If any become applicable during the study, the subject will not be required to discontinue the study, but a separate immunogenicity analysis may be done that excludes these individuals. See section 12.3 for definition of study cohorts/datasets to be evaluated.

- Use of any investigational drug or vaccine other than the study vaccine(s) during the study period.
- Chronic administration (defined as more than 14 days) of any dose level of immunosuppressants or other immune-modifying drugs during the study period and chronic daily use of inhaled steroids. Intermittent use of inhaled and topical steroids are allowed.
- Administration of a vaccine not foreseen by the study protocol during the period starting from 30 days before the first study immunization and ending 30 days after the third immunization.
- Administration of immunoglobulins and/or any blood products up to 30 days after the last study immunization.

6.6 Contraindications to vaccination

The following criteria will be checked prior to each immunization and are contraindications to further immunization. However, the study participants will be encouraged to continue to participate in the surveillance schedule for safety evaluation.

- Systemic hypersensitivity reaction following administration of the study vaccine. Severe (i.e., Grade III) local reactions will be evaluated as outlined in Sections 15.3 and 15.4 to determine whether or not further study immunizations should be administered
- Positive urine β-HCG

6.7 Indications for deferral of immunization

The following adverse events constitute grounds for temporary deferral of vaccine administration; if any one of these adverse events occurs at the time scheduled for vaccination, the subject may be vaccinated at a later date, within the time interval specified in the protocol section 7.1.7, or withdrawn at the discretion of the investigators. The subject will be followed until resolution of the event, as with any adverse event (see section 10). A subject who is withdrawn from the study, will be encouraged to remain in the safety evaluation for the duration of the study.

- Oral temperature >37.5°C or evidence of clinical malaria (see section 6.7.1) at the time of vaccination will warrant deferral of immunization until fever and symptoms resolve
- Any other condition that in the opinion of the investigator poses a threat to the individual if immunized or that may complicate interpretation of the safety of the vaccine following immunization.

Such individuals will be followed daily in the clinic until the symptoms resolve or the window for immunization expires. No further vaccination will be performed if the subject does not recover (oral temperature $\leq 37.5^{\circ}$ C and/or lack of symptoms) within 7 days of the originally scheduled vaccination date. The subject, however, will be followed for safety and immunogenicity.

If the individual meets any of the above criteria for deferral on the day of first immunization the PI may elect to exclude the subject from further participation in the study.

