6.7.1 Definition of clinical malaria

A clinical episode of *P. falciparum* malaria is defined as the presence of *P. falciparum* asexual parasitemia on Giemsa-stained thick blood smear films in the presence of the following: (i) fever defined as oral temperature $\geq 37.5^{\circ}$ C in the absence of other evident clinical conditions that could explain the fever; and/or (ii) one or more of the following symptoms consistent with malaria including but not limited to headache, vomiting, abdominal pain, or myalgia with or without fever. This case definition is based on seven continuous years of clinical experience treating children and adults with malaria in Bandiagara, and represents the current standard for clinical decisions to treat malaria in this setting. Study investigators will use their best clinical judgment in deciding when to treat malaria and will not be precluded from treating malaria by this definition.

Page 35 of 96 Version 17, DEAP/MRTC/MMVDU CONFIDENTIAL

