7.1.6 Detailed description of study visits

Day -35 to -1 Screening /inclusion of participants

Meetings will be held with town administrative and medical authorities to explain the purpose of the study. These will be followed by meetings with the traditional authorities and the heads of families for village-level "permission to enter." Subsequently, general information about the study will be disseminated through the local radio station. The target population will be invited for screening as described in investigator's subject recruiting SOPs. Screening will be performed until 60 volunteers are included.

Visit 1 (may take place over more than one visit)

Page 38 of 96 Version 17, DEAP/MRTC/MMVDU CONFIDENTIAL

- Written informed consent for screening
- Medical history of participant
- Complete physical examination
- Collect 5-10 mL venous blood sample to measure:
 - Hematology: Complete Blood Count (CBC) which includes: red blood cells, platelets, white blood cell count, lymphocyte count, hemoglobin, mean corpuscular volume and mean corpuscular hemoglobin concentration.
 - Biochemistry: serum creatinine and ALT
- Beta-HCG pregnancy test on urine for females •
- Collect urine: dipstick for blood, glucose and protein.
- Check of inclusion and exclusion criteria
- Written informed study consent for vaccination
- Assignment of unique study number
- Prepare an ID card containing participant's unique study number and photo for enrolled participants.

Day 0:

Visit 2

Vaccination 1

- Before vaccination:
- Review screening laboratory test results
- Review inclusion/exclusion criteria and check of contraindications/precautions
- Record any complaints, symptom-directed physical examination, and examination of the immunization arm(s) for any abnormalities.
- Record vital signs: oral temperature, blood pressure, pulse
- Record baseline data for solicited general symptoms
- Collect 30-40 mL venous blood sample to measure:
 - CBC, hemoglobin electrophoresis, creatinine, ALT
 - Serum for anti-AMA1 antibody titer and GIA
 - WBC for CMI to AMA1 _
- Collect urine for β-HCG test for females
- Administer study immunization 1 •

After vaccination:

- Observe for a minimum of 30 minutes
- Record blood pressure, pulse, oral temperature
- Record solicited and unsolicited events
- Instruct participants to return to the BMP clinic center immediately should they manifest any signs or symptoms they perceive as serious.

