7.1.7 Outline of study procedures

Page 43 of 96 Version 17, DEAP/MRTC/MMVDU CONFIDENTIAL

Table 3. Summary of study procedures

Study Days	-35 to -1 Screening	0	1-3	7	14	30	31- 33	37	44	60	61- 63	67	74	90	120- 364
Clinic Visit	1	2	3-5	6	7	8	9- 11	12	13	14	15- 17	18	19	20	21-23
Village & family information &	•														
discussion	•														
Written individual Screening Consent	•														
Check of inclusion/exclusion criteria	•	٠													
Check of contraindications to		•								•					
immunization		•				•				•					
Written individual Study Consent		•													
Medical history	•	٠	•	٠	٠	•	٠	•	•	•	٠	•	•	•	•
Physical examination	•	٠	•	٠	٠	•	٠	٠	•	•	٠	٠	•	•	•
Vital signs (T, BP, P)	•	\bullet^{f}	•	•	•	• f	•	•	•	\bullet^{f}	•	•	•	•	•
Vaccination		•				•				•					
Post-vaccination recording of solicited															
AE		•	•	•		•	•	•		•	•	•			
Recording of unsolicited AE occurring			_		•	-	•	•		•	-	•		-	
up to one month post-vaccination			•	•	•	•	•	•	•	•	•	•	•	•	
Recording of medication		٠	•	٠	٠	•	٠	٠	•	•	•	٠	•	•	•
Recording of SAEs during the study		•			•										
period		•	•	•	•	•	•	•	•	•	•	•	•	•	•
Urine analysis for blood, glucose and	a														
protein	•														
Urine β-HCG	● ^a	● ^b				● ^b				● ^b				•	● ^d
CBC	● ^a	•°		٠	٠	• ^c		•	•	• ^c		•	•	•	● ^d
Serum chemistry (Creatinine, ALT)	● ^a	•°		٠	٠	• ^c		•	•	• ^c		•	٠	•	● ^d
Serum and cells for anti-AMA1		• c			•	• c			•	• c			•		e
response		•			•	•			•	•			•	•	•
Monthly home visit by local guides															• ^g
Review of health status															• ^h
Scheduled blood volume (mL)	5-10	30- 40	0	5- 10	30- 40	30-40	0	5-10	30-40	30-40	0	5-10	30-40	30-40	90- 120
Cumulative Blood Volume (mL)	5-10	35-	35-	40-	70-	100-		105-	135-	165-		170-	200-	230-	320-
×)		50	50	60	100	140		150	190	230		240	280	320	440

a. Performed within 35 days prior to immunization

b. Performed just prior to each immunization

c. Blood collected just prior to each immunization

d. CBC, creatinine, ALT and urine β-HCG will be determined every 3 months from study Day 180 through study Day 364

e. Serum for anti-AMA1 antibodies and cells for CMI collected every 3 months from study Day 180 through study Day 364

f. Pre-immunization and 30mn after each immunization

g. Monthly local guides home visits to check the status of participants starting from study Day 120

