10.1.3 Recording adverse events

At each visit/assessment, the investigator will evaluate all adverse events observed by the investigators or reported by the participant. New adverse events will be recorded in the Adverse Event form within the participant's CRF. Solicited and unsolicited adverse events will be recorded on separate pages of the CRF. The nature of each event, date and time (where appropriate) of onset, outcome, intensity and relationship to vaccination will be established. Any corrective treatment will be recorded in the CRF. As a consistent method of soliciting adverse events, the participant will be asked a non-leading question such as: "Have you felt different in any way since receiving the vaccine or since the last visit?" The investigator will record only those adverse events having occurred within the time frames defined above.

Adverse events already documented in the CRF, *i.e.* at a previous assessment and designated as 'ongoing' will be reviewed at subsequent visits, as necessary. If these have resolved, the documentation in the CRF will be completed, including the date that the adverse event resolved. If an adverse event changes in frequency or intensity during a study period, a new record of the event will be started.

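### Section 6.7 permits dosing at exactly 37.5°C, a reading the protocol grades as fever, and the solicited-symptom analysis in 12.5.3 does not use the pre-dose baseline

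*Combined protocol and SAP*

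**What the plan says.** **Deferral and recovery (Section 6.7).** The deferral bullet reads "Oral temperature >37.5°C or evidence of clinical malaria (see section 6.7.1) at the time of vaccination will warrant deferral of immunization". A second bullet lets the investigator defer for any condition that threatens the participant or could cloud the safety interpretation. Three clauses then describe the end of a deferral:

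- The bullet itself: "will warrant deferral of immunization until fever and symptoms resolve".
- The follow-up sentence: "Such individuals will be followed daily in the clinic until the symptoms resolve or the window for immunization expires".
- The stopping sentence, which ends vaccination if the participant has not recovered, with recovery given as 37.5°C or below "and/or lack of symptoms) within 7 days of the originally scheduled vaccination date".

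**Fever elsewhere.** Section 6.7.1 has "fever defined as oral temperature" of 37.5°C or above. Section 10.1.4 uses the same cut-off for the solicited event. Table 5 in Section 10.2 gives grade 0 below 37.5°C and grade 1 from 37.5 to 38.0°C.

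**Baseline.** Section 7.1.6 instructs staff before each of the three doses (Visits 2, 8 and 14): "Record baseline data for solicited general symptoms". Section 7.1.3 says the same in general terms.

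**Analysis.** Section 12.5.3 plans incidence, intensity and relationship of each solicited symptom over the 7-day window, by group and dose, with two-sided Fisher's exact tests. It does not mention the pre-dose baseline. Section 12.5 leaves a final analysis plan to be agreed before database lock.

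**The concern.** Solicited symptoms are a primary endpoint (Section 12.1), and the window includes the day of vaccination. If the rule that permits a dose accepts a temperature that the endpoint calls fever, a participant can enter the window already meeting the event definition.

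The same question arises for general symptoms present before the dose. Headache and myalgia are among the malaria symptoms named in Section 6.7.1, and Section 4.3.10.1 says transmission will be rising while vaccine is given. If unchanged pre-dose symptoms are counted, the descriptive per-dose rates rise in every group and the contrast with rabies vaccine shrinks slightly. The protocol collects the record needed to separate these cases, but the analysis section gives no rule for using it.

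**Working it through.** **1. Threshold.** The rules side by side, judged on temperature alone:

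| Oral reading | 6.7 deferral (above 37.5) | 6.7 recovery (37.5 or below) | Table 5 fever grade |
|---|---|---|---|
| 37.4°C | dose | recovered | 0 |
| 37.5°C | dose | recovered | 1 |
| 37.6°C | defer | not recovered | 1 |

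The rules conflict at one value, 37.5°C. At that value:

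- A participant with parasitemia and no other evident cause of fever meets the clinical malaria definition in 6.7.1 and is deferred.
- A participant without parasitemia is deferred only if the investigator uses the second bullet.
- A participant deferred at a higher temperature who falls to 37.5°C has recovered under the stopping sentence, but is still febrile by the 6.7.1 definition.

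**2. Recovery wording.** The three clauses do different jobs. The bullet says when a deferral may end, the follow-up sentence says how long daily clinic follow-up lasts, and the stopping sentence says when vaccination ends for good. For a participant at day 7 with only one of the two problems left:

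| State at day 7 | Stop triggered if the stopping sentence means 'or' | Stop triggered if it means 'and' | Dose permitted by the deferral bullet |
|---|---|---|---|
| Above 37.5°C, no symptoms | no | yes | no |
| 37.5°C or below, symptoms persist | no | yes | no |

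The two readings differ on the permanent stop. Neither permits a dose. Section 7.1.3 also requires eligibility to be re-checked and temperature taken before each dose. For doses 2 and 3 scheduled on their target day, the ±7-day window in Table 4 closes at the same time.

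**3. Baseline.** The plan gives no figure on this point, and pre-dose symptom prevalence is not in the documents. Let p be the true post-dose rate of a symptom. Let q be the proportion with that symptom before the dose, independent of any vaccine effect and, as an unfavourable case, always counted. Then

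observed rate = p + q(1 − p), and observed difference = true difference × (1 − q).

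The illustrative starting values are 15% (malaise) and 52% (headache), the RabAvert rates in Section 4.3.11. Those are per subject, from other studies, and only anchor the arithmetic. The 40-point difference is also an assumed value.

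| Assumed q | p = 15% | p = 52% | True 40-point difference |
|---|---|---|---|
| 2% | 0.15 + 0.02 × 0.85 = 16.7% | 0.52 + 0.02 × 0.48 = 53.0% | 40 × 0.98 = 39.2 |
| 5% | 0.15 + 0.05 × 0.85 = 19.3% | 0.52 + 0.05 × 0.48 = 54.4% | 40 × 0.95 = 38.0 |
| 10% | 0.15 + 0.10 × 0.85 = 23.5% | 0.52 + 0.10 × 0.48 = 56.8% | 40 × 0.90 = 36.0 |

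In a group of 20, the expected number of added participants is 20 × q × (1 − p). For p = 15% this is 0.34, 0.85 and 1.70. For p = 52% it is 0.19, 0.48 and 0.96.

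**The case against.** **A deferral cut-off and a grading cut-off serve different purposes and need not match.** That is fair, and only one reading is affected. But the mismatch lets a participant be dosed while already meeting an endpoint definition, and changing one symbol removes it. The discretionary bullet reduces the problem without settling it.

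**The protocol already limits carry-over.** This largely stands. Section 10.1.1 defines an adverse event as a change, includes exacerbation of existing conditions, and does not require fluctuations without clinically significant worsening to be counted. Section 10.1.3 records onset, reviews ongoing events under their existing record, and says "If an adverse event changes in frequency or intensity during a study period, a new record of the event will be started". Causality is assessed for general symptoms. Table 3 heads the row "Post-vaccination recording of solicited" adverse events, so a pre-dose reading is unlikely to be the endpoint entry itself. What remains is that 12.5.3 does not say the solicited-symptom tabulation applies these rules, while Section 10.1.4 and Table 5 define fever by the absolute reading.

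**The final analysis plan may deal with it.** It may. It is not among the documents, so silence in 12.5.3 does not show that the baseline will go unused. It does make that plan a natural place to state the rule.

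**A stronger reading of the recovery wording.** A reader might infer that the stopping sentence lets staff vaccinate someone who is still ill at day 7. The text does not support that. The sentence only ends eligibility, and the deferral bullet and the pre-dose check still apply. The wording can also be read as recovery from whichever trigger caused the deferral. It is loose drafting and authorises no dose.

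**Conclusion.** The point holds as a minor one. The threshold conflict is a matter of fact and affects readings of exactly 37.5°C in participants without parasitemia who are not deferred at discretion. Replacing the 'and/or' in the stopping sentence is a consistency edit.

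The baseline gap is real but partly answered by Sections 10.1.1 and 10.1.3. Its effect on rates is expected to be small. The tabulated values depend wholly on the assumed q and on every unchanged pre-dose symptom being counted, so they illustrate and do not estimate.

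A reader might also infer a bias against or in favour of the malaria vaccine, or a lost test result. The documents support neither. Allocation is randomized and blinded within each cohort, so pre-dose symptoms should balance on average. The effect is mainly, not strictly, non-differential because the rabies recipients from two cohorts dosed at different times are analysed as one group (Section 4.3.12). Section 12.4 states that the trial is not powered for group comparisons. No sample-size figure changes.

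**What to change.** 1. In Section 6.7, defer at 37.5°C or above. Define recovery as below 37.5°C and resolution of symptoms, and use that definition in the deferral bullet, the follow-up sentence and the stopping sentence.
2. In Section 12.5.3, or in the final analysis plan before database lock, add a table by group and dose of general solicited events that are new or of higher grade than the baseline recorded at Visits 2, 8 and 14. Show it beside the all-occurrence table, which stays the main safety display.

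The cost is one wording alignment and one extra table from data already collected. The downside is that a participant reading 37.5°C on a dosing day may have the dose delayed, or lose it if the reading does not fall within the 7-day limit.
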